#### **Safety analysis**

- Safety and tolerance evaluation consist of adverse events and changes in laboratory values. Adverse

	
events were statistically described and listed in terms of occurrence, endurance, severity, relationship to the investigation product and outcome. Abnormalities in laboratory values were summarized in toxicity grade as per CTC AE 5.0. At the same time, the statistical description of the changes of the assessment values was carried out.

Study Duration
	
1.5 years

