**Withdrawal criteria**

1. PLT remains less than  $20 \times 10^9/L$  after two weeks' treatment of avatrombopag in a maximum dose of 60

	
mg/d (Solution: receive other treatment after withdrawal from the study);
 
 
2. The participant or his legal guardian requests a withdrawal ;
 
3. c poor compliance(medicine taken less than 80% of the prescribed amount or more than 120% of the prescribed amount);
 
4. With requirement of a medicine that is prohibited in the study;
 
5. With adverse events that discontinues the study;
 
6. With some unexplained serious complications;
 
7. Be pregnant during treatment;
 
8. Deemed unsuitable for further study by the investigator.
 
 
Trial Termination
 
 
1. Sponsor decides to stop the trial for safety reasons;
 
2. Independent ethics committee decides to stop the trial;
 
3. Principal investigator decides to stop the trial.
 

Investigational Product
	
 
• Name: avatrombopag;
 
• Dosage form: tablet;
 
• Specification: 20 mg/tablet.
 

Treatment Design
	
 
• The whole study is divided into two stages, including 4-weeks' core study and 4-weeks' extended study;
 
• During the core study, participants are randomly assigned into the avatrombopag group and the rhTPO treatment group(standard group) with 1:1 ratio. The initial dose of avatrombopag is 20 mg/d. If the patient's PLT count remains less than <math>20 \times 10^9/L</math> after one week, the maximum dose was increased to 40 mg/d.
 
 
Avatrombopag will be taken orally with food. The rhTPO

will be subcutaneously injected with dosage of 300 U/kg/d;

- After the end of the core study, participants in the avatrombopag group who does not meet the withdrawal indication can be enrolled in the extended study and continue the avatrombopag treatment with a maximum dose of 60 mg/d. Participants who does not respond to treatment in the rhTPO group (PLT < 20\*10^9/L ) can also be enrolled in the extended study to receive avatrombopag treatment, by titrating avatrombopag in the dose of 20-60 mg/d according to the participants' condition;

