
process
	
 
1. Informed consent;
 
2. Subject's demographic information and basic information;
 
3. Medical history, current treatment, concomitant medication;
 
4. Vital signs, physical examination;
 
5. Transplantation mode and preprocessing scheme;
 
6. Blood test: blood routine, blood biochemical (including liver and renal functions), virus infection;
 
7. Pregnancy tests (women of childbearing age);
 
8. Eligibility criteria review.
 
 
Visit 1(Day 15 after Allo-HSCT, Initial treatment)
 
 
1. Blood test: blood routine, blood biochemical (including liver and renal functions);
 
2. Vital signs, physical examination;
 
3. Concomitant medication, including PLT transfusion;
 
4. Adverse events.
 
 
Visit 2-9 (one visit per 1~2 weeks. Visit 2, day 21±2; visit 3, day 28±2; visit 4, day 35±2; visit 5, day 42±2; visit 6, day 49±2; visit 7, day 56±2; visit 8, day 62±2; visit 9, day 70±2 after Allo-HSCT)
 
 
1. Blood test: blood routine, blood biochemical (including liver and renal functions);
 
2. Vital signs, physical examination;
 
3. Concomitant medication, including PLT transfusion;
 
4. Adverse events;
 
 
(Participants who achieved PLT reconstruction during the core and extended study period directly enter the follow up period;
 
Participants who do not respond to the standard

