-----------------------	--------------------------------------------------------------------------------------------------------------------------------------------------------------------------------------------------------------------------------------------------------------------------------------------------------------------------------------------------------------------------------------------------------------------------------------------------------------------------------------------------------------------------------------------------------------------------------------------------------------------------------------------------------------------------------------------------------------------------------------------------------------------------------------------------------------------------------------------------------------------------------------------------------------------------------------------------------------------------------------------------------------------------------------------------------------------------------------------------------------------------------------------------------------------------------------------------------------------------------------------------------------------------------------------------------------------------------------------------------------------------------------------------------------------------------------------------------------------------------------------------------------------------------------------------------------------------------------------------------------

	
treatment can enter the extended study after visit 3 to receive avatrombopag treatment)
 
Visit 10 (day 28±5 after achieved PLT reconstruction)
 
 
1. Vital signs, physical examination;
 
2. Blood test: blood routine, blood biochemical (including liver and renal functions).
 
 
Long-term follow up is recommended.
 
Adverse events are closely observed and concomitant medication is recorded in detail during the study.

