
Concomitant Treatment
	
 
1. PLT transfusion is allowed according to the bleeding situation: PLT transfusion is given to participant when PLT account < 20*10^9/L, or between 21-60 *10^9/L with active bleeding;
 
2. G-CSF treatment (subcutaneous injection of G-CSF at 5 µg/kg/d from the first day after transplantation until the neutrophils count (ANC) recovered to ≥ 1*10^9/L);
 
3. Cyclosporine A, short courses of mycophenolate mofetil and methotrexate are allowed to use for the prevention of GVHD;
 
4. For medications that have been used before the trial, try to maintain the same dose during the trial;
 
5. Other TPO-RA (such as Eltrombopag and Romiplostim) should be prohibited during the study period;
 
6. Participants are allowed to take concomitant medications that are not specified as prohibited during the study period; Medications used one month prior to screening will be recorded on the case report form. All
 

	
prescription medicines, herbal medicines, nutritional supplements (including vitamins), and over-the-counter medicines should be recorded, as well as any changes in medication taken, including the dose. CYP2C9 or CYP3A4/5 medium or strong inducers may affect the exposure level of avatrombopag in vivo, and medication regimen should be comprehensively assessed by the investigator;
 
7. Observation of adverse events and concomitant medication assessment are conducted for all participants at each visit from the signing of informed consent to the end of the study;
 
8. All concomitant medications should be recorded and described in the corresponding section of the case report form (CRF).

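### Adverse events are summarised by occurrence, with no common window or time at risk, although exposure and observation depend on arm and response

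*Combined protocol and SAP*

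**What the plan says.** All references are to rows of the protocol synopsis.

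- **Safety analysis.** Adverse events "events were statistically described and listed in terms of occurrence, endurance, severity, relationship to the investigation product and outcome". No denominator, period or exposure adjustment is given. I read the second item in that list as the duration of the event, not of exposure.
- **Statistical analysis data set.** The safety set is the data from everyone with at least one dose. There is no rule for the arm or period to which a switched patient's events belong.
- **Treatment Design.** The study has two stages, "including 4-weeks' core study and 4-weeks' extended study". Avatrombopag patients who meet no withdrawal criterion "can be enrolled in the extended study and continue the avatrombopag treatment". rhTPO non-responders "can also be enrolled in the extended study to receive avatrombopag treatment".
- **Study process, visits 2–9.** "Participants who achieved PLT reconstruction during the core and extended study period directly enter the follow up period". The same note says that patients not responding to the standard "treatment can enter the extended study after visit 3 to receive avatrombopag treatment". Visit 3 is day 28±2.
- **Study process, visit 10.** This visit falls 28±5 days after reconstruction. Its list contains vital signs, physical examination and blood tests, but no adverse event item.
- **Concomitant Treatment, item 7.** "Observation of adverse events and concomitant medication assessment are conducted for all participants at each visit from the signing of informed consent", through to the end of the study.

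**The concern.** A percentage of patients with at least one event rises with the length of time they are watched. Here that time is not the same in the two arms, and it depends on the outcome. The sample size section expects 60% response on avatrombopag and 35% on rhTPO, so if the drug works as hoped, more avatrombopag patients move early to follow-up. Those who do not respond can stay on avatrombopag for up to 8 weeks, while rhTPO is given only in the core stage. After that stage, an rhTPO non-responder may be taking the other drug.

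Safety is half of the stated objective, and readers will compare the two columns of the table whether or not a test is attached. If the counting rule is left open, the same data could make either drug look worse with no true difference in toxicity.

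**Working it through.** **Figures in the plan.** The safety section states none. The response rates used below come from the sample size paragraph. The group size stated there reproduces with the unpooled two-proportion formula: (0.35×0.65 + 0.60×0.40) × (1.960 + 1.282)² / 0.25² = 78.6, rounded up to 79.

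**Inputs from the documents.** Response 60% (avatrombopag) and 35% (rhTPO); core 4 weeks; extension 4 weeks.

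**Assumptions, not in the documents.** The event hazard is constant and identical on both drugs, with a 4-week risk p of 10% to 50%. Event observation of responders ends at week t = 1 to 4. Avatrombopag non-responders are observed for 8 weeks. rhTPO non-responders contribute 4 weeks on rhTPO, or 8 weeks if their time after the switch stays in the rhTPO arm.

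**Formulas.** The risk over w weeks is f(w) = 1 − (1 − p)^(w/4).
- Avatrombopag: 0.60 f(t) + 0.40 f(8)
- rhTPO, by drug taken (randomised-drug time only): 0.35 f(t) + 0.65 f(4)
- rhTPO, by randomised arm over the whole study: 0.35 f(t) + 0.65 f(8)

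**Example, p = 20%, t = 4.** f(4) = 0.20 and f(8) = 1 − 0.8² = 0.36.
- Avatrombopag: 0.60×0.20 + 0.40×0.36 = 26.4%
- rhTPO by drug: 20.0%
- rhTPO by arm: 0.35×0.20 + 0.65×0.36 = 30.4%

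| 4-week risk | t | Avatrombopag | rhTPO by drug (ratio) | rhTPO by arm |
|---|---|---|---|---|
| 10% | 1 | 9.2% | 7.4% (1.24) | 13.3% |
| 10% | 4 | 13.6% | 10.0% (1.36) | 15.8% |
| 20% | 1 | 17.7% | 14.9% (1.19) | 25.3% |
| 20% | 4 | 26.4% | 20.0% (1.32) | 30.4% |
| 50% | 1 | 39.5% | 38.1% (1.04) | 54.3% |
| 50% | 4 | 60.0% | 50.0% (1.20) | 66.3% |

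Mean observed time explains the pattern. At t = 1 it is 0.6×1 + 0.4×8 = 3.8 weeks on avatrombopag. On rhTPO it is 0.35×1 + 0.65×4 = 2.95 weeks by drug and 0.35×1 + 0.65×8 = 5.55 weeks by arm.

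**Sensitivity to the observation rules.** Take a 10% weekly risk and reconstruction at week 3, so that 1−0.9³ = 0.271, 1−0.9⁴ = 0.344 and 1−0.9⁸ = 0.570.
- By drug taken: 0.6×0.271 + 0.4×0.570 = 39.0%, against 0.35×0.271 + 0.65×0.344 = 31.8%.
- By arm, whole study: 39.0% against 0.35×0.271 + 0.65×0.570 = 46.5%.
- By arm, responders observed to visit 10 (about week 7, 1−0.9⁷ = 0.522): 0.6×0.522 + 0.4×0.570 = 54%, against 0.35×0.522 + 0.65×0.570 = 55%.
- By drug, avatrombopag non-responders leaving at about week 6 (1−0.9⁶ = 0.469): 0.6×0.271 + 0.4×0.469 = 35%, against 32%.

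**Check of the fix, same weekly risk.** Core window only: 0.6×0.271 + 0.4×0.344 = 30.0%, against 31.8%. The remaining gap comes from responders no longer being observed after week 3. It is zero if everyone is observed for the full 4 weeks. Under the constant, equal hazard, events per patient-week are equal in either case.

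**The case against.** The strongest objection is that responders go to follow-up, not out of the study, and that item 7 of Concomitant Treatment requires event observation at each visit to study end. A reader might infer from the visits 2–9 note that events in responders are simply not collected. The documents do not support that: the visit 10 list omits events, but item 7 says otherwise. If item 7 governs, the difference by randomised arm almost disappears (54% against 55%). This objection stands as a limit on size. It does not equalise time on drug.

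Second, 8 weeks is a ceiling. Withdrawal criterion 1 concerns counts still below 20×10⁹/L after two weeks at 60 mg/d, and that dose is the stated maximum of the extension. A persistent non-responder might therefore leave at about week 6, which gives 35% against 32%. This also stands.

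Third, the summary is descriptive, and the plan nowhere says that the percentages will be unadjusted; it leaves the denominator and period open. The Statistical analysis method row does plan Kaplan–Meier and log-rank methods for transplant-related mortality, GVHD, relapse and survival. Several major transplant outcomes therefore do use time at risk, and the gap is confined to the general adverse event summary.

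What is left is that no row gives a window, a time at risk or an attribution rule for that summary, in a design where all three matter.

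**Conclusion.** The concern holds as a defect in how the safety comparison is specified. With equal toxicity on both drugs, percentages by occurrence can differ, and the counting of the extension decides which drug looks worse. By drug taken, the avatrombopag to rhTPO ratio is about 1.04 to 1.36 over 4-week risks of 10% to 50% and responder exit at weeks 1 to 4. By randomised arm over the whole study the order reverses, at 18–26% against 25–30% for a 20% risk. These figures rest on a constant hazard, on assumed risks and exit times, and on the observation rules. They show what can happen and are not a forecast.

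Two stronger readings should be resisted. A reader might infer that the plan is biased against avatrombopag by a known amount. It is not: both the sign and the size depend on rules that the plan does not give, and under one reading the gap is negligible. A reader might also infer an inflated error rate. No between-arm adverse event test is planned, so type I error is not affected. The damage is to the interpretation of the safety table.

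**What to change.** 1. Make the main safety comparison by randomised arm over the common 4-week core window from day 15. Report both the percentage of patients with an event and events per patient-week under observation.
2. Tabulate extended-study and post-switch events separately, as avatrombopag exposure, per patient-week. Keeping the periods apart also helps if risk changes with time since transplant, because a rate pooled over both stages would then mix periods.
3. Reconcile Treatment Design with the Study process note on when rhTPO patients may switch: after the 4-week core, or after visit 3 at day 28, about 13 days after day 15. Until this is settled, the later part of the core window in the rhTPO arm may contain avatrombopag time.
4. Reconcile the visit 10 list with item 7 of Concomitant Treatment on event collection, so that time at risk is defined for responders.
5. Make sure that the CRF records event onset dates. The documents imply this but do not state it.

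The cost is SAP wording, one more column in the tables and a check of the CRF. The downside is that later events leave the headline comparison, so the separate extension table must be reported alongside it.
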